## 4.2. SECONDARY EFFICACY PARAMETERS

Analysis of the following secondary efficacy parameters is no longer applicable in the study:

- the tumour response and disease control rates in both arms,
- the duration of response, the duration of disease control, time to treatment failure and time to first response in both arms,
- the overall survival in both arms.

## 5. SAFETY PARAMETERS

### 5.1. ADVERSE EVENTS

Each patient will be assessed for occurrence of adverse events. The CTCAE version 3.0 will be used. Adverse events not classified by the CTCAE will also be reported and graded according to their severity: mild (grade 1), moderate (grade 2), severe (grade 3), life-threatening or disabling (grade 4), sudden death (grade 5), not applicable in case of progression or adverse event not gradable according to CTCAE and leading to dose modification (NA).

Treatment Emergent Adverse Event (TEAE) will be considered for analysis of adverse effects. A TEAE is defined as any event that first occurred during the treatment period (i.e. from first drug administration date up to last administration date + 30 days) or that “worsened” during that study period. The definition of “worsening” is described below:

- Any increase in the grade (according to CTCAE) compared to baseline adverse event,  
or
- Any adverse event becoming serious during the study period, or

- Any adverse event not pre-treated at baseline requiring a corrective treatment during study, or
- Any adverse event requiring a modification of the study drug administration, or
- Any adverse event becoming possibly, probably or definitely related to the study drug

An adverse event that meet one of the criteria described above will be considered as TEAE and reported in the analyses for the reminder of the study, even if the TEAE downgrades to baseline situation.

Baseline situation of the pre-treatment adverse events will be determined by using:

- the worst grade of the adverse event during the pre-study period (within 2 weeks prior to treatment),
- the seriousness of the event during the pre-study period,
- the use of corrective treatment (even if stopped at the day of first administration) during the pre-study period.

This situation will be used as comparator to determine whether an existing adverse event during study period becomes treatment-emergent (i.e. if at least one of these previous parameters gets worst during study treatment).

The adverse events and signs and symptoms will be classified using the Medical Dictionary for Regulatory Activities (MedDRA). The implementation of this international terminology in the Oracle Clinical® database will be performed using the available version of MedDRA. Each description of the toxicity (verbatim) will be associated with the five following items:

- System Organ Class (SOC),
- High Level Group Term (HLGT),
- High Level Term (HLT),
- Preferred Term (PT),
- Lowest Level Term (LLT).

The matching of the adverse events reported on the CRF pages with the baseline pre-treatment events to determine the qualification for TEAE will be done by using the Lowest Level Term of the MedDRA dictionary and the qualification for TEAE will be implemented by the study statistician on a dataset provided by the data manager and containing all AEs reported on the CRF pages or derived by the study data manager according to CRF completion guidelines.

Two sets of events will be considered:

- all adverse events regardless of relationship to treatment,
- the adverse events that are possibly, probably or definitely related to treatment,
- If the causality is missing, the AE will be considered as related to study treatment

A cycle will be evaluable for non-haematological toxicity if the following criteria are fulfilled:

- At least one drop or one tablet of any treatment was given,
- The toxicity has been assessed by the investigator during the cycle.

A patient will be evaluable for non-haematological toxicity if at least one cycle is evaluable and will be analysed in the treatment arm she was effectively treated.

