
 1. Patients with known or with clinical evidence of brain metastasis or leptomeningeal involvement 2. Patients with pulmonary lymphangitis or symptomatic pleural effusion (grade ≥ 2) that results in pulmonary dysfunction requiring active treatment. 3. Patients having received any other experimental drug or chemotherapy within 30 days before randomisation. 4. History of second primary malignancy, except: bilateral breast carcinoma, in situ carcinoma of the cervix, adequately treated non melanomatous carcinoma of the skin, and other malignancy treated at least 5 years previously with no evidence of recurrence. 5. Patients with pre-existing motor/sensory peripheral neuropathy of NCI CTCAE version 3.0 grade > 1. 6. Patients having received > 3 regimens of chemotherapy 7. Prior therapy with capecitabine and/or vinca alkaloids (including vinflunine) 8. History of severe hypersensitivity to vinca alkaloids and/or to fluoropyrimidine or any contra indication to any of the study drugs. 9. Known or suspected dihydropyrimidine dehydrogenase (DPD) deficiency. 10. A female is not eligible to enter the study if: pregnant or lactating or with positive pregnancy test at inclusion. 11. Female of childbearing potential who is unwilling or unable to use a medically accepted method to avoid pregnancy during the 2 months preceding the start of study treatment, throughout the study period and at least 3 months following the last dose of study treatment. 12. Known history of HIV infection. 13. Inability to take and/or absorb oral medication including previous gastric surgery or any evidence of partial oesophageal, gastric, small or large bowel obstruction; gastrointestinal disorder that affect the absorption of capecitabine (malabsorption syndrome, 2/3 gastric resection and bowel resection). 14. Patients who have any serious, concurrent uncontrolled medical disorder especially uncontrolled hypercalcaemia, congestive heart failure, uncontrolled high-risk hypertension, arrhythmia, angina pectoris or previous history of myocardial infarction within 6 months prior to randomisation 15. Prior bone marrow transplantation or autologous stem cell infusion following high-dose chemotherapy.. 		
Study L00070 IN 311 B0		3/5

Name of SPONSOR: Pierre Fabre MEDICAMENT		
Name of finished product:	JAVLOR®	
Name of active substance(s):	VINFLUNINE DITARTRATE	

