#### Pre-treatment events

- Pre-treatment events according to MedDRA Preferred Term (PT) and System Organ Classification (SOC),

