## **11.2. ADVERSE EVENTS**

### **11.2.1. All adverse events**

The incidences of the treatment-emergent adverse events (TEAE) as defined in 5.1, graded according to NCI-CTCAE version 3.0 will be presented using the MedDRA SOC and PT defined during the MedDRA coding process.

A summary table will provide by treatment arm the following:

- On treatment deaths
- Patients with at least one AE
- Patients with at least one TEAE (overall and by grade)
- Patients with at least on SAE
- Patients with at least one TEAE leading to discontinuation
- Patients with at least one TEAE requiring dose interruption and/or adjustment
  - Patients with at least one TEAE requiring dose interruption
  - Patients with at least one TEAE requiring dose adjustment
- Patients with at least one TEAE requiring additional therapy
- Cycles with at least one AE
- Cycles with at least one TEAE (overall and by grade)

Overall incidences per patient and per cycle will be depicted as well as the incidence of non related and related toxicities only. An analysis will also present the CTCAE grade presented for each SOC and PT per patient and cycle according to the relationship with study treatment.

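### TEAE status is decided at MedDRA Lowest Level Term but reported at Preferred Term, so an unchanged baseline symptom later coded to another LLT can be counted as treatment-emergent

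*SAP*

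**What the plan says.** SAP 5.1 defines the flag: "A TEAE is defined as any event that first occurred during the treatment period", or that worsened in that period. Worsening is judged against a baseline made up of the worst grade, seriousness and use of corrective treatment in the two weeks before treatment.

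The same section describes the coding: "Each description of the toxicity (verbatim) will be associated with the five following items", and lists SOC, HLGT, HLT, PT and LLT in that order. The step that links on-study events to their baseline counterparts "to determine the qualification for TEAE will be done by using the Lowest Level Term of the MedDRA dictionary". The study statistician applies it to a dataset supplied by data management. A flagged event stays a TEAE for the rest of the study "even if the TEAE downgrades to baseline situation".

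Reporting is at a higher level. Under SAP 11.2.1, TEAE incidences "will be presented using the MedDRA SOC and PT defined during the MedDRA coding process". The pre-treatment events in SAP 9.1.2 are likewise summarised by PT and SOC, and the tables in Appendix 1 follow the same levels.

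**The concern.** The LLT is the level nearest to the words on the CRF, and more than one LLT can sit under a single PT. If a symptom is recorded in one way before treatment and in another way at a later cycle, the two records may carry different LLTs. The LLT rule then finds no baseline event. The baseline grade, seriousness and treatment are never compared, and the record can count as a first occurrence. The same patient would appear under one PT in the pre-treatment table and again under that PT as treatment-emergent, with nothing having worsened. That defeats the purpose of the baseline comparator.

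Carried-over symptoms are plausible here. All patients have had an anthracycline and a taxane, and protocol exclusion criterion 5 removes only patients with "pre-existing motor/sensory peripheral neuropathy of NCI CTCAE version 3.0 grade > 1", so grade 1 neuropathy may enter.

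Safety is the only secondary objective still evaluated. SAP section 12 drops the adverse events of special interest and the constipation analysis on the ground that full AE tables will be produced, so those tables carry the safety result. Incidence is also given per cycle, so one wrong flag can recur.

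**Working it through.** The plan states no figure on this point, so there is nothing to reproduce. The check compares the two matching rules and then illustrates the possible size.

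**Step 1: the rules on the same record.** Take a patient with a grade 1 symptom before treatment and the same symptom at grade 1 on study. It is not serious, not newly treated, led to no change in study drug and was judged unrelated.

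| Coding of the on-study record | LLT matching (SAP 5.1) | PT matching |
|---|---|---|
| Same LLT as baseline | matched, not a TEAE | matched, not a TEAE |
| Different LLT, same PT | unmatched, can be flagged as first occurrence | matched, not a TEAE |
| Different PT | unmatched, can be flagged | unmatched, can be flagged |

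The rules differ only in the second row.

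**Step 2: direction.** The PT-level baseline is the worst over all LLTs under that PT, so it is at least as severe as the baseline of any one LLT. On first occurrence, grade, seriousness and corrective treatment, LLT matching can therefore only add TEAEs relative to PT matching.

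**Step 3: which counts move.** SAP 5.1 makes an event a TEAE if it becomes related to study drug, and it treats missing causality as related. An unchanged symptom judged related, or with causality missing, is therefore a TEAE under either rule. So is one that leads to a study drug modification, or one that is treated on study after going untreated at baseline. The difference falls on unchanged events judged unrelated, so mainly on low-grade, all-causality counts.

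**Step 4: illustrative size for one PT.** Inputs:
- Patients per arm: 112 randomised 1:1 (SAP 1 and 2), so 112 / 2 = 56. The safety set is treated patients, so this is approximate.
- b, the share of patients with an unchanged baseline symptom of that PT: not in the documents, assumed.
- q, the probability that the on-study report is coded to another LLT of that PT: not in the documents, assumed.

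Expected false TEAE patients per arm = 56 × b × q.

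| b | q | Patients per arm | Percent of arm |
|---|---|---|---|
| 10% | 5% | 56 × 0.10 × 0.05 = 0.3 | 0.5% |
| 20% | 10% | 56 × 0.20 × 0.10 = 1.1 | 2% |
| 30% | 20% | 56 × 0.30 × 0.20 = 3.4 | 6% |
| 40% | 30% | 56 × 0.40 × 0.30 = 6.7 | 12% |
| 50% | 40% | 56 × 0.50 × 0.40 = 11.2 | 20% |

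Rows two and four are the working range; the first and last show how far the answer moves with the assumptions. Under PT matching the count from this source is 0 in every row.

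**The case against.** Several points on the other side have force.

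- **Rewording alone is not enough.** A reader might infer that any symptom described in new words becomes a false TEAE. The text does not support that: two wordings coded to one LLT still match. The definition also speaks of when an event first occurred, and onset dates are collected. The SAP does not say how dates and LLT matching combine, so a persisting symptom with a pre-treatment onset might be caught. This stands, and it limits the claim to what can happen.
- **Unseen guidelines may help.** SAP 5.1 refers to CRF completion guidelines that are not in the documents. If they carry a continuing event forward under one term, a change of LLT would be rare. This also stands, though the SAP does not say that they do.
- **Drug-related tables.** A reader might infer that these are inflated too, especially where causality is missing. They are little affected, for the reason in step 3 of the working.
- **Limited consequence.** The analyses are descriptive, the rule is the same in both arms, and calculated laboratory grades have their own shift tables. The pre-treatment and AE listings let a reader compare records by hand. All of this is true, but it does not correct the summary tables.
- **LLT matching errs towards counting events, which is defensible for safety.** PT matching alone errs the other way: it can hide a truly new event of the same PT at the same or a lower grade. This stands, and it is why PT matching needs a review step.

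**Conclusion.** The mismatch is in the text: matching at LLT, reporting at PT, and no visible fallback to PT, harmonisation of LLTs or review of unmatched synonyms. An unchanged baseline symptom coded to another LLT of the same PT can therefore be counted as treatment-emergent.

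The size cannot be derived from the documents. The range of 1.1 to 6.7 patients per arm for one PT is arithmetic on assumed rates; the wider assumptions give 0.3 to 11.2. It also presumes that neither onset dates nor the CRF guidelines remove the problem.

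A reader might infer that one arm is made to look worse. The documents show no direction between arms, and no test or error rate depends on this flag. It is a modest defect in the tables for the one secondary objective that remains, and it is cheap to correct.

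**What to change.** In SAP 5.1, match pre-treatment and on-study events at PT and leave the worsening rules as they are. Before the TEAE flag is final, list every on-study event that shares a PT but not an LLT with a baseline event of the same patient, showing reported terms, grades and onset dates. Have it reviewed medically without knowledge of arm, so that a truly new event (for example at another site) stays a TEAE. The trial is open-label, so the listing should leave out arm and study drug details.

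An acceptable alternative is to keep LLT matching and let the same review remove false flags. Either way, 5.1 should state how onset dates enter the decision.

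The cost is a short edit to 5.1, a change to the TEAE program, one listing and some review judgement. Recording each reclassification with its reason would keep that judgement open to checking.

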## **5.2. FEBRILE NEUTROPENIA**

According to CTCAE version 3.0, febrile neutropenia (FN) is defined as ANC  $<1.0 \times 10^9/L$  and fever  $\geq 38.5^\circ C$  of unknown origin without clinically or microbiologically documented infection. (§ 5.4.1. "General considerations" of the protocol).

## **5.3. HAEMATOLOGICAL PARAMETERS**

Haematological toxicity will be assessed by laboratory investigations of haemoglobin, WBC, ANC and platelets. Grades will be calculated according to CTCAE version 3.0.

A cycle will be evaluable for haematological toxicity analysis if the following criteria are fulfilled:

- At least one drop or one tablet of any treatment,
- At least one blood cell count between Day 2 and Day 1 of next cycle or end of treatment period for the last administered cycle,
- At least one of the four haematological parameters analyzed has been measured.

A patient is evaluable for haematological toxicity analysis if at least one cycle is evaluable.

## **5.4. BIOCHEMICAL PARAMETERS**

Biochemical toxicity will be assessed by laboratory investigations of liver function tests (i.e. bilirubin, alkaline phosphatase, SGOT/AST, SGPT/ALT), renal function tests (creatinine) and metabolic function tests (sodium, potassium, calcium). Grades will be calculated according to the CTCAE version 3.0.

A cycle will be evaluable for biochemical toxicity analysis if the following criteria are fulfilled:

- At least one drop or one tablet of any treatment has been administered,
- At least one biochemistry test between Day 2 and Day 1 of next cycle or end of treatment period for the last administered cycle,
- At least one of the eight biochemical parameters analysed has been measured.

A patient will be evaluable for biochemical toxicity analysis if at least one cycle is evaluable.

In addition, SGOT/AST, SGPT/ALT and bilirubin will be analyzed according to the presence or not of liver lesions at baseline in order to assess the relationship between liver metastasis and worst grade during study.

The same analysis will be done for Alkaline Phosphatase according to the presence or not of liver/bone metastases.

## **6. OTHER PARAMETERS**

### **6.1. CONCOMITANT MEDICATIONS PARAMETERS**

In the same way as the adverse events, concomitant medications will be coded using the specific international terminology WHO-Drug Dictionary version 2007, March 1.

If the start and end dates are both anterior to randomization date will be analysed as prior concomitant medication. Otherwise, the treatment will be considered as concomitant medication.

## **7. DEFINITION OF POPULATIONS**

According to Protocol amendment PA06, all statistical analyses will be performed on the Intent-to-treat (ITT) population. Other populations will not be constituted.

### **7.1. INTENT-TO-TREAT POPULATION**

All randomised patients will be included in the intent-to-treat population. They will be analysed in the arm they were assigned by randomisation.

### **7.2. ELIGIBLE POPULATION**

No longer applicable for the study.

### **7.3. EVALUABLE POPULATION FOR RESPONSE**

No longer applicable for the study.

### **7.4. EVALUABLE POPULATION FOR SAFETY**

All treated patients will be included in the safety analysis. They will be analysed in the treatment arm they actually received.

## **8. STATISTICAL METHODS**

### **8.1. STATISTICAL SOFTWARE AND METHODOLOGY**

Most analyses will be carried out with 9.3 version of SAS® for Windows® (or later version if available). All statistical tests will be two-sided at a 5% level of significance unless specified otherwise.

All baseline descriptive statistics will be presented in summary tables by treatment arm and overall.

Continuous data will be summarized with the following items: frequency, median (if  $n \geq 3$ ), min, max, mean and standard deviation if relevant.

Categorical data will be presented in contingency tables with frequencies and percentages of each modality (including missing data modality).

### **8.2. STATISTICAL METHODS FOR CATEGORICAL VARIABLES**

The  $\chi^2$  test will be performed to compare proportions or replaced by Fisher's exact test if the expected frequency in one cell of the contingency table is less than 5. The 95% confidence interval for proportions will be computed following the exact method. If a stratified analysis is required a Cochran-Mantel-Haenszel (CMH) test will be used (option CMH in the TABLES statement of the FREQ procedure in SAS).

### **8.3. STATISTICAL METHODS FOR ORDINAL VARIABLES**

Comparisons between the two treatment arms will be provided for ordinal data using the non-parametric Wilcoxon rank sum test.

### **8.4. STATISTICAL METHODS FOR CONTINUOUS VARIABLES**

The distributions of quantitative data will be examined by the Kolmogorov-Smirnov test in order to test for normality. In case of Gaussian distribution, the comparison between the 2 treatment arms will be made with a Student t-test. If the distribution is not considered as Gaussian then the non-parametric Wilcoxon test will be performed.

### **8.5. STATISTICAL METHODS FOR TIME DEPENDENT DATA**

To describe time dependent parameters, Kaplan-Meier curves and life tables by treatment arm will be provided. Confidence intervals on the median will be calculated using the Brookmeyer and Crowley

method. Hazard ratio and 95% confidence intervals will be reported. A stratified Cox proportional model will be performed to compare the two treatment arms taking into account the stratification factors (except centre) used at the time of randomisation.

## 9. TREATMENT GROUP DESCRIPTION

### 9.1. DESCRIPTION AT BASELINE

Analysis of baseline characteristics and demography will be performed on the ITT population, by treatment arm.

#### 9.1.1. Overview of the study

The reasons for treatment discontinuation will be reported. Study discontinuation will be described according to the following reasons: adverse event (related or not), death (related or not), progressive disease, lost to follow up, protocol deviation and other reasons.

The patient status (dead, alive, lost to follow-up ) at the cut-off date will be displayed together with each reason of death (progressive disease, adverse event, other).

The number of patients randomised, treated will be presented by treatment group and overall.

Time between randomisation and first administration will be tabulated by treatment arm.

The duration of follow-up is defined as the time elapsed between the date of randomisation and the date of last news or death, death being a censored observation.

#### 9.1.2. Characteristics at baseline

Demographic and baseline characteristics of patients will be displayed. The following variables will be analysed on the ITT population according to the arm assigned at randomisation:

##### Demographic data

- Age at the time of randomisation
- Categorized groups of age :< 35, [35 – 50[, [50 – 65[, [65 – 75[, [75 – 80[ and ≥ 80 years,
- Karnofsky performance status at baseline in categorical data,
- Body weight,
- Body surface area.
- Menopausal status (defined by the presence of the term “Menopause” in the Medical History)

Last available value will be used for baseline analysis.

##### Stratification data Extract from the IVRS database

- Categorized groups of performance status (“70-80” vs. “90-100”) at randomisation,
- Visceral disease (“yes” vs. “no”) at randomisation.

##### Disease history:

Characteristics at diagnosis:

- Primary site of cancer: right / left / bilateral
- Histological type: carcinoma / ductal/ lobular /inflammatory/ other (with specification)
- TNM classification,
- SBR grade.

Characteristics at study entry:

- Hormonal receptors at study entry: hormonal receptor ER+/- (positive/negative/unknown or not done), hormonal receptor PR+/- (positive/negative/unknown or not done),
- HER-2 status at study entry (IHC method): 0/1+/2+/3+/missing/not done,
- HER-2 status at study entry (FISH/CISH method): negative/positive/missing/not done,
- Hormone receptors and HER-2 status (triple negative\* versus HR positive\* and HER-2 negative versus HR positive or negative\*),
- Extent of the disease at study entry (locoregional disease/metastatic disease),
- Measurable disease
- Categorized groups of number of organs involved: 1, 2 and  $\geq 3$  organs,
- Detail of organs involved.
- Time from initial diagnosis to study entry,
- Progression-free interval,
- Categorized groups of progression-free interval:  $\leq 4$  months /  $> 4$  months,
- Disease-free interval,
- Categorized groups of disease-free interval:  $\leq 12$  months /  $> 12$  months
- Treatment free interval,

\* : **Triple negative** patients are those presenting with HER2-, PgR- and ER-  
**HR positive** patients are those presenting with PgR+/- and ER+ or PgR+ and ER+/-  
**HR negative** patients are those presenting with PgR- and ER-  
**HR positive or negative** patients are those presenting with PgR+/- and ER+/-

Measurable disease defined as:

- Yes if the number of targeted lesions is  $> 0$ ,
- No if number of targeted lesions is not  $> 0$  and the number of non-targeted lesions is  $> 0$
- No disease in other cases

The progression free interval is the time interval elapsed between the date of end of the last prior chemotherapy given in the metastatic setting and the date of relapse or progression after this last line of chemotherapy. This progression free interval of patients relapsing or progressing during the last line treatment will be estimated to last one day.

The disease free interval is the time interval elapsed between the date of end of the last prior chemotherapy according to intents neo-adjuvant/adjuvant and the date of relapse or progression.

The treatment free interval is the time elapsed between the date of end of the last treatment (prior chemotherapy, prior hormone therapy..., whichever occurs last) and the first administration of study treatment.

